6 RESEARCH QUESTION AND OBJECTIVES

This study will characterize the real-world effectiveness of pembrolizumab (monotherapy or in combination with platinum-based chemotherapy [PBC], separately) for the treatment of NSCLC across races, ethnicities, and age groups. Population, Intervention, Comparison, Outcomes, Time, and Study design (PICOTS) criteria are provided in [Table 1](#) and detailed inclusion and exclusion criteria are listed in Section 7.2.

Primary study objectives:

1. To evaluate the real-world effectiveness of **pembrolizumab monotherapy** in US patients with **early-stage NSCLC** by estimating real-world overall survival (rwOS) among the following subgroups:
 - Race (e.g., Black or African American, Asian, other [American Indian/Alaska Native, Native Hawaiian/Other Pacific Islander, and other race] and White patients)
 - Hispanic/Latino ethnicity (Hispanic/Latino patients and not Hispanic/Latino patients)
 - Age (elderly patients ≥ 75 years and younger patients < 75 years)
2. To evaluate the real-world effectiveness of **pembrolizumab in combination with PBC** in US patients with **early-stage NSCLC** by estimating rwOS among the above subgroups
3. To evaluate the real-world effectiveness of **pembrolizumab monotherapy** in US patients with **advanced NSCLC** by estimating rwOS among the above subgroups
4. To evaluate the real-world effectiveness of **pembrolizumab in combination with PBC** in US patients with **advanced NSCLC** by estimating rwOS among the above subgroups

Exploratory study objectives:

1. To evaluate the real-world effectiveness of pembrolizumab monotherapy (see Primary Objective 1) and pembrolizumab in combination with PBC (see Primary Objective 2) in US patients with **early-stage NSCLC** by estimating **real-world disease-free survival (rwDFS) and real-world event-free survival (rwEFS)**, respectively, among the above subgroups
2. To apply **propensity score methods** to the evaluation of the real-world effectiveness of pembrolizumab monotherapy (see Primary Objective 3) and pembrolizumab in combination with PBC (see Primary Objective 4) in US patients with **advanced NSCLC** among the above subgroups

PRODUCT: MK-3475	PROTOCOL/AMENDMENT VERSION NO.: 00-v03
REVOPS ID NO: NIS104408	NIR DRC APPROVAL DATE: 11/24/2025
EPIDEMIOLOGY NO.: EP05026.164	

Table 1 PICOTS criteria

PICOTS	Inclusion	Exclusion
Population	Adults (≥ 18 years of age) diagnosed with early-stage or advanced NSCLC	Prior treatment with an IO agent or an investigational drug Treatment with pembrolizumab in combination with any of the following: concurrent chemoradiation therapy; radiation therapy, or an investigational drug
Intervention	Received pembrolizumab (monotherapy or in combination with platinum-based chemotherapy [PBC]) for the treatment of NSCLC	Participation in clinical trials for NSCLC before pembrolizumab Treatment with pembrolizumab in the second-line setting or later
Comparison	No formal statistical comparisons	
Outcomes	Real-world overall survival (rwOS) among the following subgroups: 
 Race (e.g., Black or African American, Asian, other [American Indian/Alaska Native, Native Hawaiian/Other Pacific Islander, and other race] and White patients) Hispanic/Latino ethnicity (Hispanic/Latino patients and not Hispanic/Latino patients) Age (elderly patients ≥ 75 years and younger patients < 75 years) Real-world disease-free survival (rwDFS) in early-stage NSCLC patients (exploratory) Real-world event-free survival (rwEFS) in early-stage NSCLC patients (exploratory)	
Time	Patients initiating pembrolizumab between October 2, 2015 (first FDA approval of pembrolizumab for NSCLC) and June 30, 2025 (allows patients to accumulate ≥ 2 years of follow-up time to adequately assess rwOS); Data cutoff planned June 30, 2027	
Study design	Retrospective cohort study using structured EHR-derived data	

PRODUCT: MK-3475	PROTOCOL/AMENDMENT VERSION NO.: 00-v03
REVOPS ID NO: NIS104408	NIR DRC APPROVAL DATE: 11/24/2025
EPIDEMIOLOGY NO.: EP05026.164	

7 RESEARCH METHODS

7.1 Study Design

This retrospective cohort study will utilize electronic health record (EHR)-derived databases that are largely representative of the US NSCLC population and include sizable racial and ethnic minorities and elderly patients. A two-phased feasibility assessment is ongoing, with Phase 1 having been completed January 2025. Phase 1 of the feasibility assessment addressed data availability and determined whether a data source appropriately addressed the study objectives, and led to the selection of Flatiron Health. Phase 2 includes a comprehensive assessment to evaluate the reliability and relevancy of Flatiron data, with assessment concluding by April 2026.

7.2 Setting

Adult patients diagnosed with NSCLC and treated with pembrolizumab (monotherapy or in combination with PBC) between October 2, 2015 (first FDA approval of pembrolizumab for NSCLC) and June 30, 2025 in the US will be eligible for inclusion in this study. Eligible patients will be identified from two Flatiron databases: the early non-small cell lung cancer (eNSCLC) Flatiron Health Research Database (FHRD) and advanced non-small cell lung cancer (aNSCLC) FHRD. Early-stage and advanced NSCLC patients will be analyzed separately. Details of each database are described in Section 7.4.

The follow-up time for each patient in this study spans from the start of patient activity in the database through the date of death (if any) or last confirmed activity date through June 30, 2027 (data cutoff). In the proposed study design, patients will have opportunity to accumulate ≥ 2 years of follow-up time for outcome ascertainment through June 30, 2027.

Inclusion criteria

- Diagnosis of NSCLC (any stage)
 - Patients initially diagnosed with early-stage NSCLC (Stage I-IIIA or IIIB with known surgical resection).
 - Patients initially diagnosed with advanced NSCLC (Stage IIIB- IV), or who were previously diagnosed with eNSCLC and subsequently developed recurrent or progressive disease.
- Age 18 years or older at the time of NSCLC diagnosis
- Received ≥ 1 cycle of pembrolizumab (monotherapy or in combination with PBC) for the treatment of NSCLC
 - Patients with evidence of treatment with pembrolizumab as monotherapy or in combination with PBC as neoadjuvant and/or adjuvant therapy for eNSCLC will be selected from the eNSCLC FHRD.

PRODUCT: MK-3475	PROTOCOL/AMENDMENT VERSION NO.: 00-v03
REVOPS ID NO: NIS 104408	NIR DRC APPROVAL DATE: 11/24/2025
EPIDEMIOLOGY NO.: EP05026.164	

- Patients with evidence of treatment of pembrolizumab as monotherapy or in combination with PBC as first-line therapy in the advanced setting will be selected from the aNSCLC FHRD.
- Pembrolizumab initiation date between October 2, 2015 and June 30, 2025 (to allow ≥ 2 years of follow-up time)
- Known (non-missing) race, ethnicity, or age (depending on the subgroup of interest)

Exclusion criteria

- Prior treatment with an IO agent or an investigational drug on or before initiation of pembrolizumab
 - Patients selected from the aNSCLC FHRD who received treatment with an IO agent (including pembrolizumab) or an investigational drug before the initiation of pembrolizumab *in the advanced setting* will be excluded.
- Treatment with pembrolizumab in combination with any of the following: concurrent chemoradiation therapy (CCRT), radiation therapy (RT), or an investigational drug
 - Patients treated with pembrolizumab as monotherapy or in combination with PBC in the neoadjuvant or adjuvant setting with evidence of CCRT or RT will be excluded based on abstracted RT data.
 - Patients treated with pembrolizumab as monotherapy or in combination with PBC in the advanced setting will be assumed to not concurrently be receiving CCRT or RT.
- Treatment with pembrolizumab in the second-line setting or later
 - Patients selected from the aNSCLC FHRD who were treated with pembrolizumab in the second-line setting (or later) will be excluded.

Eligible patients will meet the inclusion and exclusion criteria listed above. Patients will not be excluded if they have a prior cancer diagnosis (including lung cancer), receive pembrolizumab outside of NCCN guidelines or approved indications (i.e., off-label or compassionate use), or participate in clinical trials that include treatment with an investigational drug for NSCLC after treatment with pembrolizumab.

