7.3.2 Outcomes

Health outcomes: Clinical events or outcomes which may be represented as diagnoses, treatment or procedures (examples include syncope, disease progression or hypoglycemia collected as study endpoints, or death). Any herein described health outcomes, collected per the protocol, will be summarized as part of any interim analysis (if required) and in the final study report.

The primary outcome of interest for the current study will be death, as measured by rwOS, defined as the time from pembrolizumab treatment start to date of death. rwOS is a validated endpoint to measure the effectiveness of advanced cancers, including NSCLC [Lasiter, L., et al 2022] [Curtis, M. D., et al 2018], and some early-stage cancers, such as breast cancer [Zhang, Q., et al 2021]; however, rwOS has not yet been validated for early-stage NSCLC. Patients without a date of death will be censored on the date of the last follow-up or data cutoff date (June 30, 2027), whichever occurs first. A composite mortality variable that already exists in the FHRDs will be used. This composite mortality variable represents a patient's vital status and date of death, combining publicly available Social Security Death Index (SSDI) data and obituary data (processed from obituaries, funeral homes and other sources) with the EHR-derived mortality data (i.e., structured date of death and abstracted information from available EHR documentation) [Curtis, M. D., et al 2018] [Zhang, Q., et al 2021]. Separate estimates of rwOS will be provided for each of the following: race, ethnicity, and age group.

In the eNSCLC FHRD, analyses of rwDFS and rwEFS as exploratory endpoints will be conducted for each of the following subgroups: race, ethnicity, and age group. The rwDFS endpoint assesses time from the date of a patient's surgery with evidence of complete resection to first instance of local recurrence, distant recurrence, progression, or death. rwEFS assesses the time from index date (i.e., pembrolizumab therapy start date) to first instance of local recurrence, distant recurrence, progression, or death. For both endpoints, patients without an event will be censored on the date of the last follow-up or data cutoff date (June 30, 2027), whichever occurs first. Both analyses will leverage composite variables derived from EHR data elements, although neither outcome has been validated in the eNSCLC FHRD.

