7.5 Study Size

The study will include all patients in the research databases who meet study inclusion and exclusion criteria within the data cutoff period. Early-stage NSCLC analyses will include fewer patients and events than advanced NSCLC analyses given the more recent pembrolizumab approvals in early-stage populations. [Table 2](#) includes preliminary sample size estimates of patient subgroups, stratified by stage group (i.e., FHRD database), as of April 30, 2025. Sample sizes do not account for stratification by treatment type (pembrolizumab monotherapy vs. pembrolizumab in combination with PBC), therefore the number of patients included in each subgroup will be further reduced in the final analysis.

Table 2 Preliminary estimates of study sample size, by stage group

Eligible patient population (as of April 30, 2025)	Early-stage NSCLC Stage I-IIIA + Resected IIIB [eNSCLC FHRD]	Advanced NSCLC Stage IIIB-IV [aNSCLC FHRD]
Adult NSCLC patients	10,787	109,074
Received pembrolizumab	1,244	25,623
Race		
Asian	24	531
Black or African American	103	2,737
White	893	17,298
Other or Unknown	222	5,017
Ethnicity		
Hispanic or Latino	41	918
Not Hispanic or Latino	914	18,802
Unknown	289	5,903
Age		
<75 years	627	12,922
≥75 years	617	12,701

PRODUCT: MK-3475	PROTOCOL/AMENDMENT VERSION NO.: 00-v03
REVOPS ID NO: NIS104408	NIR DRC APPROVAL DATE: 11/24/2025
EPIDEMIIOLOGY NO.: EP05026.164	

As this study will be descriptive in nature, no hypothesis tests or formal power calculations will be performed. Assuming an expected median OS of 1.67 years (20 months) that is consistent across all subgroups, precision estimates (95% CI) are provided for each subpopulation across a range of overall sample sizes.

Table 3 Estimates of precision for expected median OS (1.67 years), by overall sample size and expected proportion of subpopulations

Subpopulation proportion	N=1,000 95% CI	N=2,500 95% CI	N=5,000 95% CI	N=7,500 95% CI	N=10,000 95% CI
2% (Asian)	(0.98-3.48)	(1.17-2.58)	(1.29-2.25)	(1.35-2.12)	(1.39-2.05)
5% (Hispanic or Latino)	(1.17-2.58)	(1.32-2.17)	(1.41-2.01)	(1.46-1.94)	(1.48-1.9)
13% (Black or African American)	(1.33-2.16)	(1.44-1.96)	(1.50-1.87)	(1.53-1.83)	(1.55-1.81)
85% (White)	(1.46-1.92)	(1.57-1.78)	(1.60-1.74)	(1.61-1.73)	(1.62-1.72)
41% (≥ 75 years)	(1.52-1.84)	(1.53-1.82)	(1.57-1.78)	(1.59-1.76)	(1.6-1.74)

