Real-world OS as defined in Section 7.3.2 will be estimated among patients using Kaplan-Meier methods. Median survival times and the probabilities of survival at key milestones of interest (e.g., 1-year, 5-year, etc.) and corresponding 95% confidence intervals (CI) will be calculated. Separate analyses will be conducted for each the following subgroups: Black or African American, Asian, other race, White, Hispanic/Latino, not Hispanic/Latino, elderly (≥ 75 years), and younger (<75 years). Racial subgroups with small sample sizes (<75 patients) may be combined with 'other race'. A descriptive summary of rwOS estimates will be provided for all races, ethnicities, and age groups. Given the descriptive nature of the study, no imputation for missing data or statistical testing will be performed. Sensitivity analyses may be conducted to evaluate the effectiveness of pembrolizumab among the subset of patients receiving pembrolizumab in line with currently approved indications (i.e., on-label use).

Exploratory analyses of rwDFS and rwEFS as defined in Section 7.3.2 will be conducted in the early-stage NSCLC population. The rwDFS endpoint will be evaluated among patients analyzed in Primary Objective 1 (i.e., surgically-resected patients who did not receive neoadjuvant therapy prior to surgery). The rwEFS endpoint will be evaluated among patients analyzed in Primary Objective 2 (i.e., resectable patients who received neoadjuvant therapy). For both outcomes Kaplan-Meier methods will be used to estimate median survival times and the probabilities of survival at key milestones of interest and corresponding 95% CI will be calculated. Separate analyses will be conducted for each race, ethnicity, and age group. Sensitivity analyses may be conducted to evaluate the effectiveness of pembrolizumab among the subset of patients receiving pembrolizumab in line with currently approved indications.

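### Cohort 2 admits neoadjuvant stage IIIB patients only if they are later resected, which builds immortal time into early-stage rwOS and rwEFS

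*Protocol*

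**What the plan says.** Protocol section 7.2 (Setting, inclusion criteria) puts into the early-stage group "Patients initially diagnosed with early-stage NSCLC (Stage I-IIIA or IIIB with known surgical resection". It does not say whether the resection must precede pembrolizumab. The Table 2 header in section 7.5 carries the same rule: "Stage I-IIIA + Resected IIIB". The other stage group in section 7.2 is "Patients initially diagnosed with advanced NSCLC (Stage IIIB- IV), or who were previously diagnosed with eNSCLC and subsequently developed recurrent or progressive disease".

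Section 7.3.2 sets time zero. Death is the primary outcome, "as measured by rwOS, defined as the time from pembrolizumab treatment start to date of death". For the exploratory endpoint, "rwEFS assesses the time from index date (i.e., pembrolizumab therapy start date) to first instance of local recurrence, distant recurrence, progression, or death". Section 7.8 names the population: "The rwEFS endpoint will be evaluated among patients analyzed in Primary Objective 2 (i.e., resectable patients who received neoadjuvant therapy". The indications listed in section 5 place neoadjuvant pembrolizumab plus chemotherapy before surgery.

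Section 7.4 describes the eNSCLC database as confirming stage I-IIIA disease and does not mention IIIB. Section 7.8 has no landmark analysis, delayed entry or classification by intent, and section 7.10 does not list the issue among the limitations.

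**The concern.** Take two stage IIIB patients who start the same neoadjuvant combination on the same day. One is resected and belongs to cohort 2. The other dies, or progresses and loses surgery, and does not meet the early-stage definition. Follow-up for both would have begun at the first dose, so what happens during follow-up decides who is in the cohort. Between first dose and surgery, a IIIB patient in cohort 2 cannot die.

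Primary Objective 2 (rwOS in cohort 2) is affected, not only exploratory rwEFS. Section 7.10 offers the exploratory endpoints as mitigation for immature early-stage survival data, yet in cohort 2 that endpoint has the same fault. The patients left out might also reappear among the advanced patients on combination therapy (cohort 4), if their course is read as first-line advanced therapy. Assigning each patient to one database only does not remove the problem, because the fault lies in when membership is decided.

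**Working it through.** **No plan figure to reproduce.** The protocol gives no number that depends on this rule. Table 2 has 1,244 early-stage patients who received pembrolizumab, not split by treatment type or by individual stage. The IIIB share, the share not reaching surgery, the time to surgery and the survival values below are all assumptions.

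**Timing, by patient type**

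| Patient | Needed to be early-stage | When it is known |
|---|---|---|
| Stage I-IIIA, neoadjuvant | stage | before time zero |
| Stage IIIB, surgery before pembrolizumab | stage and resection | before time zero |
| Stage IIIB, neoadjuvant | stage and resection | resection only after time zero |

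Only the third row conditions on the future.

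**Check A: one hazard for everyone.** Survival is exponential, w is the IIIB share, and IIIB patients are kept only if event-free at surgery time t. Then

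S_rule(24) = S(24) / [(1 − w) + w·S(t)].

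- Largest case (median 20 months, t = 5, w = 30%): S(24) = 0.435 and S(5) = 0.841. The denominator is 0.70 + 0.30 × 0.841 = 0.952, so S_rule is 0.457, a bias of 2.18 points.
- Smallest case (median 60 months, t = 3, w = 5%): S(24) = 0.758 and S(3) = 0.966. The denominator is 0.998 and the bias is 0.13 points.

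Within IIIB alone, 24-month survival is overstated by about 3 to 8 points over medians of 20 to 60 months and surgery at 3 to 5 months. The IIIB median is overstated by exactly t.

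**Check B: unresected IIIB patients do worse.** Let f be the share of IIIB not resected, and s0, s1, s2 the 24-month values for stage I-IIIA, resected IIIB and unresected IIIB. Then

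S_all = (1 − w)s0 + w[(1 − f)s1 + f·s2]

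S_rule = [(1 − w)s0 + w(1 − f)s1] / [(1 − w) + w(1 − f)].

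Assumed values are EFS 62%, 55%, 10% and OS 80%, 75%, 40%, with f = 10-30%. For w = 20% and f = 20%:

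- EFS: S_all = 0.496 + 0.2 × (0.44 + 0.02) = 0.588; S_rule = (0.496 + 0.088)/0.96 = 0.608; bias 2.0 points.
- OS: S_all = 0.64 + 0.2 × (0.60 + 0.08) = 0.776; S_rule = (0.64 + 0.12)/0.96 = 0.792; bias 1.6 points.

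**Whole-cohort bias at 24 months, in percentage points**

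| IIIB share | Check A | Check B, EFS | Check B, OS |
|---|---|---|---|
| 5% | 0.13 to 0.35 | 0.26 to 0.78 | 0.20 to 0.60 |
| 20% | 0.52 to 1.43 | 1.01 to 3.06 | 0.78 to 2.36 |
| 30% | 0.78 to 2.18 | 1.50 to 4.53 | 1.16 to 3.50 |

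Within IIIB, Check B gives 4.5 to 13.5 points for EFS and 3.5 to 10.5 for OS. The direction is upward in every case, including the common-hazard case, where nothing but immortal time is at work.

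**The case against.** The best defence is that the effect may be very small. If the stage I-IIIA description in section 7.4 governs, few or no IIIB patients enter from the eNSCLC database. Stage I-IIIA patients, and those operated on before pembrolizumab, are untouched. rwEFS is exploratory and unvalidated, and no formal comparisons are planned. All of this stands and limits the weight of the point. It does not remove it, because section 7.2 and Table 2 both admit resected IIIB.

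A reader might infer more than the protocol supports:

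- *IIIB patients are 100% event-free at surgery by construction.* True for survival only. Section 7.3.2 counts progression as an event, and a patient can progress and still be resected.
- *Every unresected patient has had an event.* Missing surgery is not itself an rwEFS event. With 20% IIIB and 20% unresected, treating all unresected patients as events (same event share in every stage) gives 0.80/0.96 = 83.3% against 80.0% at surgery, 3.3 points. If only half have an event, it is (0.72 + 0.16)/0.96 = 91.7% against 90.0%, 1.7 points.
- *The bias flatters patients aged 75 or older.* Section 5 says elderly patients tend to be treated less intensively. It says nothing about the chance of reaching surgery once neoadjuvant treatment has begun.
- *The failures are moved into cohort 4.* Section 7.2 takes from the aNSCLC database only patients given pembrolizumab first-line in the advanced setting. A neoadjuvant course may not qualify, and the patient may then be in no cohort.

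**Conclusion.** The point holds for neoadjuvant stage IIIB patients in cohort 2. Their membership depends on an event after time zero, and cohort 2 rwOS and rwEFS are biased upward as a result. The direction is well supported; the size is not known. Under assumed IIIB shares of 5-30% it is roughly 0.1 to 4.5 points for the whole cohort at 24 months, and at the low end if IIIB is rare. Subgroups could be affected unequally if the IIIB share or the chance of reaching surgery differs between them, but the protocol gives no figure for either.

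The statistical analysis plan was not available. The inclusion criterion, however, is fixed in the protocol, so this is not a detail left for later. The point should be corrected; it does not undermine the study as a whole.

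**What to change.** Take one of two routes in section 7.2.

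1. Define early-stage membership by facts known at pembrolizumab start: stage I-IIIA, or stage IIIB resected before pembrolizumab initiation.
2. If neoadjuvant IIIB patients with later resection are kept, let them enter the risk set only from the surgery date (delayed entry), and report cohort 2 restricted to stage I-IIIA as a sensitivity analysis. Delayed entry removes the immortal time. It does not undo selection of patients who were fit to reach surgery, which is why the restricted analysis is needed beside it. For rwEFS, a patient who progressed before surgery has already had the event and cannot enter at surgery as event-free.

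Either way, align the advanced-stage definition, the Table 2 header and the stage I-IIIA database description in section 7.4, and reconcile the resectable patients of section 7.8 with the resected ones of section 7.2. State where neoadjuvant IIIB patients outside cohort 2 go. Under route 1 those resected later still fit the stage IIIB-IV definition and could default into cohort 4.

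Surgery date is already a listed variable (section 7.3.1), so no new data are needed. The cost is a few lines of protocol text and cohort programming, and some IIIB patients leave cohort 2 or contribute only post-surgery follow-up. The stage I-IIIA result describes a different population and need not be lower. With the values assumed in Check B it would be 62% for EFS, against 60.8% under the present rule.

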- Although the same patient may be present in both eNSCLC and aNSCLC FHRD databases, the exclusion criteria pertaining to prior treatment ensure that each patient will only be included in the study sample once. Patients included in the eNSCLC FHRD who received pembrolizumab in both the early- and advanced-stage settings will only be included if they meet all eligibility criteria at earliest initiation of pembrolizumab (i.e., in the early-stage setting), while patients included in the aNSCLC FHRD who have evidence of treatment with pembrolizumab in both the early- and advanced-stage settings will not be included.
- Study inclusion/exclusion criteria are intended to reflect a real-world patient population. As such, study populations may not mirror the corresponding clinical trial populations and, as a result, observed results may not be comparable to those reported using clinical trial data. Sensitivity analyses may be conducted to evaluate the effectiveness of pembrolizumab among subsets of patients receiving pembrolizumab in line with currently approved indications (i.e., on-label use).
- Mortality data may not have sufficient maturity for all patients. For example, OS among patients with early-stage NSCLC recently treated with pembrolizumab may be particularly likely to be impacted by limited data maturity, affecting interpretability. Exploratory outcomes rwEFS and rwDFS will be evaluated for early-stage patients to mitigate the limitation in data maturity. Since neither outcome has been validated for use in the eNSCLC FHRD, results should be interpreted with caution.

Generalizability of study results:

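### As written, the second-line exclusion for advanced patients is not tied to their first pembrolizumab, so a literal filter would select on a post-index event that requires survival

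*Protocol*

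**What the plan says.** Three statements in the protocol fix who enters the advanced cohorts.

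- Section 7.2, inclusion, for the advanced database: "Patients with evidence of treatment of pembrolizumab as monotherapy or in combination with PBC as first-line therapy in the advanced setting will be selected".
- Section 7.2, exclusion: "Patients selected from the aNSCLC FHRD who were treated with pembrolizumab in the second-line setting (or later) will be excluded".
- Section 6, Table 1, Intervention row, exclusion column: "Treatment with pembrolizumab in the second-line setting or later".

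The exclusion names no first, initial or index exposure in either place. Other rules do carry a time reference. The prior-immunotherapy exclusion in 7.2 concerns patients "who received treatment with an IO agent (including pembrolizumab) or an investigational drug before the initiation of pembrolizumab" in the advanced setting. The closing paragraph of 7.2 says that patients are not excluded if they "participate in clinical trials that include treatment with an investigational drug for NSCLC after treatment with pembrolizumab"; later pembrolizumab is not on that list. Section 7.10 says that patients in the early-stage database who received pembrolizumab in both settings "will only be included if they meet all eligibility criteria at earliest initiation of pembrolizumab", but it does not extend this to line of therapy within the advanced cohorts.

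Section 7.3.2 sets time zero: rwOS is "defined as the time from pembrolizumab treatment start to date of death".

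**The concern.** Take a patient who starts pembrolizumab first-line for advanced disease, meets every inclusion criterion, and later receives it again in a second or third line. On the words of 7.2 and Table 1 this patient was treated with pembrolizumab in the second line or later and is excluded. The ground for exclusion arises after the survival clock has started, and only a patient who lives into a later line can acquire it. Patients who die during first-line treatment can never be removed this way.

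If the filter were programmed literally, the Kaplan-Meier estimates for Primary Objectives 3 and 4 would come from a cohort partly selected on its own future. The exploratory weighting in section 7.8 balances baseline characteristics and cannot restore patients removed for a later event.

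The sentence must be applied by another organisation. Section 7.9 gives selection of the study cohort to the data supplier, and the checks in section 7.7 test programs against their specification. A specification that copied the literal rule would pass those checks.

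**Working it through.** **Step 1. What can the exclusion remove?** Sort advanced-database patients by the lines in which they received pembrolizumab in the advanced setting.

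- First line only: included, not touched by the exclusion.
- Second line or later only: never meet the first-line inclusion rule, so they are already out.
- First line and again later: meet the inclusion rule and are caught by the literal exclusion.

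Within the set that the inclusion rule selects, the third group is the only one on which the exclusion can act. Read as a mirror of the inclusion rule, it removes nobody further and is redundant.

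**Step 2. Is it anchored elsewhere?** The prior-immunotherapy rule is anchored before initiation. The tolerated post-index events include later trial participation but not later pembrolizumab. The earliest-initiation wording in 7.10 covers early-stage database patients. Nothing supplies an anchor for the advanced cohorts.

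**Step 3. Illustration of the literal reading.** The protocol states no figure for this, so there is none to reproduce. Inputs:

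- Median OS of 20 months: section 7.5.
- Exponential survival, S(t) = 2^(-t/20): assumption.
- Share p of the whole cohort removed: assumption, 2-10%.
- Time s at which every removed patient is still alive: assumption, 6, 12 or 24 months. Removed patients are drawn at random from those alive at s.

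Survival in the patients kept:

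- for t ≤ s: (S(t) - p) / (1 - p)
- for t > s: S(t) × [1 - p/S(s)] / (1 - p)

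Full cohort: S(12) = 0.660, S(60) = 0.125, median 20.0 months.

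*p = 10%, s = 12.* One-year survival is (0.660 - 0.10)/0.90 = 0.622. Beyond 12 months the multiplier is (1 - 0.10/0.660)/0.90 = 0.943. The median solves S(t) = 0.5/0.943 = 0.530, so t = 18.3 months. Five-year survival is 0.125 × 0.943 = 0.118.

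*p = 5%, s = 12.* The multiplier is (1 - 0.05/0.660)/0.95 = 0.973, so S(t) = 0.514 and the median is 19.2 months. One-year survival is 0.642.

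*p = 2%.* The median is 19.9 months for s = 6, 19.7 for s = 12 and 19.4 for s = 24, a shift of 0.1 to 0.6 month.

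A simulation of 2,000,000 patients gave the same values to within rounding.

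**Step 4. Does the direction hold under another model?** An illness-death simulation let patients move from first line to second line (median 14 months) or death (median 24 months), with median survival of 10 months after second line starts, and removed 20% of second-line starters. All inputs are assumed.

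| Scenario | Median, months | 1-year | 5-year |
|---|---|---|---|
| No long-term survivors | 17.2 to 16.3 | 63.5% to 61.5% | 4.5% to 4.2% |
| 20% long-term survivors who never start second line | 21.5 to 21.2 | 69.5% to 68.6% | 17.7% to 19.0% |
| As the row above, 6-month median after second line starts | 18.1 to 18.1 | 64.8% to 64.4% | 15.7% to 17.2% |

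With a long-term-survivor fraction, 1-year survival still falls, the median may barely move, and 5-year survival rises, because the removed patients are drawn from those who progressed.

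**Step 5. Scale against Table 3.** At N = 10,000 the half-widths are (1.72 - 1.62)/2 = 0.05 year, or 0.6 month, for White patients; (1.81 - 1.55)/2 = 0.13 year, or 1.6 months, for Black or African American patients; 0.21 year, or 2.5 months, for Hispanic or Latino patients; and 0.33 year, or 4.0 months, for Asian patients. The shifts of 0.8 month (5%) and 1.7 months (10%) from step 3 exceed the first. Only the 10% case reaches the second, and neither reaches the last two.

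**The case against.** The best defence is that the sentence is simply the reverse side of the first-line inclusion rule. In Table 1 it sits in the Intervention row, opposite receipt of pembrolizumab, where it describes the studied treatment and not the patient's later history. Sections 7.2 and 7.3.2 work from pembrolizumab initiation throughout. On that reading no first-line initiator is lost and the bias is zero. This is probably what the sponsor meant, and it stands as an account of intent. It does not rescue the wording, because on that reading the exclusion does nothing and on the other it does harm.

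A second defence is that section 7.8 leaves operational details to the SAP. That holds for how lines of therapy are derived, including whether an added agent opens a new line. Eligibility itself is fixed in 7.2 and Table 1.

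A third is that loose timing is not unique to this rule: the exclusion of pembrolizumab combined with an investigational drug also lacks an anchor. That is fair, and this sentence should not be presented as the sole exception.

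A reader might also infer that the advanced age contrast would be distorted, since section 5 reports less intensive treatment in elderly patients. That text says nothing about pembrolizumab re-treatment by age, and Table 1 plans no formal comparisons, so the documents do not support the inference.

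**Conclusion.** The exclusion is badly worded and should be corrected. As written, it can act only on first-line initiators who were treated again, which makes eligibility for two of the four primary objectives depend on surviving to a later line.

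A reader might go further and conclude that these patients will be removed and that advanced rwOS is biased downward. The documents do not support that. Removal happens only if the sentence is applied literally, and the intended reading gives no bias. Under literal application a fall in median and 1-year rwOS is the expected direction, but 5-year survival, a milestone named in section 7.8, can move either way.

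The size is not derivable, because no re-treatment rate is given. The illustrative medians of 19.2 to 18.3 months rest on an assumed 5-10% removed, all alive at 12 months, and on exponential survival. At 2% the shift is 0.1 to 0.6 month. In the largest groups such a shift can exceed the sampling error in Table 3; in the smallest it stays below it.

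**What to change.** In section 7.2 and in the matching cell of Table 1, state that patients whose first pembrolizumab in the advanced setting was given in the second line or later are excluded, and that patients who initiated it as first-line therapy remain eligible regardless of pembrolizumab received in any later line.

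Keep the change to this criterion. A general instruction to judge every advanced-cohort criterion only on information up to the index date is not needed, and it could disturb the classification of combination therapy where a partner drug starts after the first pembrolizumab dose.

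The cost is one sentence, one table cell and the corresponding cohort filter. No new data are needed. If the sponsor already intended the first-exposure reading, the cohort does not change; otherwise the advanced cohorts become somewhat larger. It is best done before data extraction.
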